# Iron Endpoints Subjects who used i.v. and oraliron • Number of subjects who used i.v. and/or oral iron will be summarized • Subjects who used i.v. and oral iron will be defined as follows:

• Subjects with on-therapy i.v. and/or oral iron medication collected in a specific eCRF form (CONMEDS-IRON).

#### **Quarterly IV Iron Dose**

- Records of on-therapy iron medication will be used for the following calculations
- Monthly average i.v. iron by quarter = Total i.v. iron dose during each quarter (mg) / (duration in a quarter (days) / 30.4375 days).
- Total i.v. iron dose during each quarter (mg) will be carried with the following formula using each record. Duration will be derived from iron medication start/stop date:
  - Total i.v. iron dose in each quarter (mg) = (iron dose1\*frequency1\*duration1) + ... + (iron dosen\*frequencyn\*durationn)

 $\circ$  Duration (days) = (stop date1 - start date1 + 1) + ... + (stop daten - start daten + 1) Frequency is defined as follows:

- If subject receives iron dose with once daily  $\rightarrow$  frequency = 1
- If subject receives iron dose with BID  $\rightarrow$  frequency = 2
- If subject receives iron dose with TID  $\rightarrow$  frequency = 3
- If subject receives iron dose with QID  $\rightarrow$  frequency = 4
- Quarters will be defined as follows:
  - Quarter 1:start date = Randomization Date
    - end date = Treatment Start Date at Week 12 1 (day)
  - Quarter 2:start date = Treatment Start Date at Week 12 end date = Study Treatment Stop Date
  - If treatment start date at Week 12 is missing (i.e. early withdrawal before Week 12), the end date of Quarter 1 will be replaced with Study Treatment Stop Date. Quarter 2 will not be generated.
  - Iron medication start/stop date will be defined newly for the analyses in addition to Quarter start/end date to derive amount of iron dose within a specified quarter (analysis flags may be used to judge which quarters the iron records should belong to).
- If iron medication start date < randomization date, the iron medication start date will be replaced with randomization date for the analyses.
- If iron medication end date > Study Treatment Stop Date, the iron medication stop date will be replaced with Study Treatment Stop Date for the analyses.
  - If iron medication start date and stop date step over quarters, the iron medication record will be divided; the end date in the former record and the start date in the latter record will be replaced with the guarter end date and the next guarter start date, respectively.

Quarter State of Iron Medication	Definition
Quarter 1	Iron Medication End Date ≤ Quarter 1 End Date
Quarter 2	Quarter 2 Start Date ≤ Iron Medication Start Date
Quarter 1 & 2 (will be divided as described above)	Iron Medication Start Date ≤ Quarter 1 End Date and
	Quarter 2 Start Date ≤ Iron Medication Stop Date

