3. OBJECTIVES AND ENDPOINTS

Objectives	Endpoints
Primary	

 To characterize the appropriateness of the starting dose of GSK1278863 in HD patients not using ESAs 	
 Change from baseline in Hgb at Week 4 Number (%) of subjects by Hgb change from baseline category at Week 4
Secondary	

 To characterize overall Hgb control of GSK1278863 in HD patients not using ESAs 	
 Hgb and changes from baseline Number (%) of subjects who have a Hgb level within the target range (10.0–12.0 g/dL) Time (in days) to reach the lower target Hgb level (10.0 g/dL) Number (%) of subjects who have a Hgb level of less than 7.5 g/dL Number (%) of subjects who have a Hgb increase of more than 2 g/dL over any 4 weeks Number (%) of subjects who have a Hgb level of more than 13.0 g/dL and number of episodes

 To characterize the PK of GSK1278863 	
 AUC and Cmax of plasma GSK1278863

 To characterize the effect on iron use of GSK1278863 	
 Dose of intravenous iron Number (%) of subjects who used intravenous iron

 To characterize the effect on iron metabolism of GSK1278863 	
 Change from baseline in ferritin Change from baseline in TSAT Changes from baseline in hepcidin, serum iron, and TIBC

 To characterize dose adjustment of GSK1278863 	
 Distribution of dose level Duration of treatment interruption due to Hgb > 13 g/dL Frequency of dose adjustments
Safety	

 To assess the safety and tolerability of GSK1278863 	
 Incidence and severity of AEs and SAEs, including AESIs Reasons for discontinuation of study medication Laboratory tests, ECG, vital signs, and ophthalmology assessments

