6.10. Concomitant Medications and Non-Drug Therapies

Concomitant medications, including over-the-counter medications and supplements, taken during the study will be recorded in the eCRF. Start/stop dates will be recorded for general concomitant medications, while additional details, including dose, route of administration, and dosing frequency, will be recorded for certain medications (e.g., ESAs, iron). Refer to SRM for further details.

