#### NOTES:

- Only on-therapy iron medication will be evaluated.
- If no start or stop date is recorded on iron medication, the date will be replaced with Randomization Date or Study Treatment Stop Date, respectively.

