#### 10.7.2.1. Handling of Missing and Partial Dates

Element	Reporting Detail
General	Partial dates will be displayed as captured in subject listing displays.
Concomitant Medications /Dialysis	
 
Partial dates for any concomitant medications recorded in the CRF will be imputed using the following convention:
 
If the partial date is a start date, a '01' will be used for the day and ' lap' will
 

/Dialysis	be used for the month
	
 
If the partial date is a stop date, a '28/29/30/31' will be used for the day (dependent on the month and year) and 'Dec' will be used for the month.
 

	The recorded partial date will be displayed in listings.

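### The i.v. iron formula has no frequency below once daily and can overstate such dosing; its stop-date imputation counts a one-off infusion once for every imputed day

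*SAP*

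**What the plan says.** "Dose of intravenous iron" is a secondary endpoint in Protocol section 3. SAP 8.1.2 summarises it by quarter with mean, SD, quartiles, minimum and maximum.

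SAP 10.6.3, Quarterly IV Iron Dose, gives the derivation: "Total i.v. iron dose during each quarter (mg) will be carried with the following formula using each record". Each record contributes dose × frequency × duration, and "Duration will be derived from iron medication start/stop date", as stop minus start plus one day. The sum is divided by (days in the quarter / 30.4375) to give a monthly average. Four frequencies are defined, from "If subject receives iron dose with once daily" (1), through two and three times a day, to "If subject receives iron dose with QID" (4). A record that crosses the Week 12 boundary is divided between quarters.

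Three rules govern dates:

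- The notes to the same derivation: "If no start or stop date is recorded on iron medication, the date will be replaced with Randomization Date or Study Treatment Stop Date", respectively. There is no exception for a single infusion.
- SAP 10.7.2.1, for a partial stop date: the month's last day "will be used for the day (dependent on the month and year) and 'Dec' will be used for the month".
- SAP 10.6.3 again: an iron stop date later than Study Treatment Stop Date is pulled back to it.

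On data capture, Protocol 6.10 says "additional details, including dose, route of administration, and dosing frequency, will be recorded for certain medications (e.g., ESAs, iron") and refers to the SRM for details. Protocol 6.11 leaves route and dose of iron to the investigator and fixes no schedule.

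**The concern.** The multiplier list suits a drug taken every day. Every defined value is at least 1 per calendar day, so on a date-range record with less-than-daily dosing any of them can only overstate. The date rules push the same way: they assume that a record without a stop date describes continuing use, which is wrong for one infusion.

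The endpoint is meant to describe iron use on the study drug in a small cohort: Protocol 4.3 expects 22 enrolled and 17 completing Week 24. I.v. iron is not to be used before Week 4 (Protocol 4.2), and supplementation is triggered only when ferritin and TSAT are both low (Protocol 6.11), so the number of users may be small. One wrong record could then set the maximum and move the mean and SD.

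**Working it through.** The plan gives no i.v. iron total, so there is no figure to reproduce. I applied the SAP formula to example records.

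**Assumptions (not in the documents):** 40 mg per infusion, which cancels in every ratio; 84-day quarters, with Quarter 2 starting on Day 85; Study Treatment Stop Date on Day 168; frequency coded 1 wherever the true schedule is less than daily.

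**1. Date-range record, frequency 1.** SAP total = dose × days. Iron given = dose × (doses per week / 7) × days. The long-run ratio is 7 / doses per week.

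| Schedule | SAP total over 84 days | Iron given | Ratio |
|---|---|---|---|
| Three times weekly | 3,360 mg | 1,440 mg | 2.33 |
| Twice weekly | 3,360 mg | 960 mg | 3.5 |
| Weekly | 3,360 mg | 480 mg | 7 |
| Every two weeks | 3,360 mg | 240 mg | 14 |

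Records that start and end on a dosing day give slightly lower ratios:

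- Eight weekly doses span 7 × 7 + 1 = 50 days: 40 × 50 = 2,000 mg against 8 × 40 = 320 mg (6.3 times).
- Three doses a week for four weeks, Monday to Friday, span 26 days: 40 × 26 = 1,040 mg against 12 × 40 = 480 mg (2.2 times).

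**2. One infusion, stop date missing, frequency 1.** Duration = 168 − start day + 1, and the ratio equals that duration.

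| Infusion on | Days counted | SAP total | Iron given |
|---|---|---|---|
| Day 29 | 140 | 5,600 mg | 40 mg |
| Day 57 | 112 | 4,480 mg | 40 mg |
| Day 85 | 84 | 3,360 mg | 40 mg |
| Day 141 | 28 | 1,120 mg | 40 mg |
| Day 168 | 1 | 40 mg | 40 mg |

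For the Day 57 infusion, 28 days (1,120 mg) fall in Quarter 1 and 84 days (3,360 mg) in Quarter 2, when no iron was given.

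**3. One infusion, partial stop date, frequency 1.** If only the day is missing, duration = days in month − infusion day + 1. An infusion on the 5th of a 30-day month counts 26 times. If the month is missing too, the date becomes 31 December, cut back to Study Treatment Stop Date. When treatment stops before year end, that gives the same result as a missing date.

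**4. Effect on the summary.** For one Day 85 infusion with no stop date, the Quarter 2 monthly value is 3,360 / (84 / 30.4375) = 1,217.5 mg, against a true 40 / (84 / 30.4375) = 14.5 mg. The excess of about 1,203 mg raises the cohort mean by about 71 mg with 17 subjects, or 55 mg with 22.

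**5. Record with stop equal to start, frequency 1.** Duration is 1 and the total is exact: twelve such records give 12 × 40 = 480 mg, as given.

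**The case against.** A reader might infer that the SAP overstates weekly or per-session i.v. iron as a matter of course. The documents do not support that. The SAP leaves the frequency of such iron undefined and does not say to use 1. It sums over records, and if each infusion is its own one-day record the total is right. The recording convention may be in the SRM, which is not among the documents. Nor do they state an iron schedule: the Monday-Wednesday-Friday example in Protocol 7.1 concerns the choice of study visit day.

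It can also be said that start and stop dates are to be collected (Protocol 6.10), that data are cleaned before freeze (SAP 3.2), that quartiles are reported beside the mean, that Listing 35 shows iron records by subject, and that the count of iron users does not use this formula. The endpoint is descriptive, with no test attached.

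All of this limits the size and likelihood of the error. It does not remove the gap. No text requires one record per infusion, and the SAP provides for multi-day records by dividing them at the quarter boundary. Nor does one record per infusion cure the date rules: a one-off infusion with a blank stop date is exactly what they extend. For a one-off infusion, 1 is the only multiplier that makes a complete record correct, so it is the natural value to use, and the imputed duration then produces the error.

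**Conclusion.** The point holds in two parts of different strength.

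- **Less-than-daily dosing:** the formula is undefined. It can overstate by about 2.3 times (three times weekly) or 7 times (weekly), but only if the iron is entered as a date range and coded 1.
- **One-off infusion without a full stop date:** with frequency 1, the written rules give a wrong total unless the imputed date happens to equal the infusion date. For a missing date the factor is the days left to treatment stop: 28 to 140 for infusions from Day 141 back to Day 29, under the Day 168 assumption.

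The documents do not show how often either case will arise. This is a correction to one secondary endpoint's derivation, worth making before database freeze. It does not touch the primary endpoints.

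**What to change.** In SAP 10.6.3, for i.v. iron only:

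1. Compute the total as dose per administration × number of administrations falling in the quarter. Take the number from one record per infusion, or derive it from the recorded frequency and dates.
2. For a single-administration record with a missing or partial stop date that cleaning does not resolve, set the stop date equal to the start date.
3. Keep the run-to-treatment-stop imputation only for records documented as ongoing repeat dosing.

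Use a count of administrations; simply adding fractional multipliers to the existing duration falls short. In the examples above, 40 × 1/7 × 50 = 286 mg against 320 mg (11% low), and 40 × 3/7 × 26 = 446 mg against 480 mg (7% low). Rounding the count up to a whole dose repairs both: 50/7 = 7.1 becomes 8, and 26 × 3/7 = 11.1 becomes 12. Count over the whole record, then allocate doses to quarters by date, so that a record crossing Week 12 is not rounded twice.

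The cost is a few lines of SAP text and some programming. No new data are needed, since Protocol 6.10 already collects dose, route and frequency for iron.

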#### NOTES:

- Only on-therapy iron medication will be evaluated.
- If no start or stop date is recorded on iron medication, the date will be replaced with Randomization Date or Study Treatment Stop Date, respectively.

#### TIBC

TIBC will be calculated automatically by the central laboratory using:
 TIBC = UIBC + total iron

#### TSAT

- Based on literature review the distribution of TSAT is skewed and requires a log-transformation. Calculation of statistics on log-transformed data are described in Section 10.5.2.2.
- TSAT will be calculated automatically by the central laboratory using:
  - TSAT = 100 \* (Serum Iron/TIBC)

#### Hepcidin

• Based on literature review the distribution of hepcidin is skewed and requires a logtransformation. Calculation of statistics on log-transformed data are described in Section 10.5.2.2.

#### 10.6.4. Safety

#### Adverse Events

#### AE up to Week 4

Cut-off date of Week 4 for individuals will be based on Week 4 visit date which is associated with the earliest date throughout Week 4 records (i.e., SDTM.SVSTDTC).

#### **AE of Special Interest**

AEs of special interest are manually-selected at patient-level (i.e. following case-by-case review by members of the SRT including representatives from the local Japan team) and not at preferred term level.

Adverse events of special interest are classified as follows:

- Thrombosis and/or tissue ischemia secondary to excessive erythropoiesis
- Death, MI, stroke, heart failure, thromboembolic events, thrombosis of vascular access
- Cardiomyopathy
- Pulmonary artery hypertension
- Cancer-related mortality and tumor progression and recurrence
- Esophageal and gastric erosions
- Proliferative retinopathy, macular edema, choroidal neovascularization
- Exacerbation of rheumatoid arthritis

#### **CV** Events

Basically, patient profiles of CV events will be provided according to records captured in eCRF, except for Peripheral Arterial Thrombosis Embolism (PAT) form.

CV events in PAT form will be provided only when a related AE sequence number is not present. This is because several records in PAT form are captured just for AESI information, instead of CV events.

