7.4.1.4. Cardiovascular and Death Events

For any CV events detailed in Section 12.6. and all deaths, whether or not they are considered SAEs, specific CV and Death sections of the CRF will be required to be completed. These sections include questions regarding CV (including sudden cardiac death) and non-CV death.

The CV CRFs are presented as queries in response to reporting of certain CV Medical Dictionary for Regulatory Activities (MedDRA) terms. The CV information should be recorded in the specific CV section of the CRF within one week of receipt of a CV Event data query prompting its completion.

The Death CRF is provided immediately after the occurrence or outcome of death is reported. Initial and follow-up reports regarding death must be completed within one week of when the death is reported.

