# 10.14.12. Patient Profile Listings

Patient Profile Listings							
No.	Population	IDSL / TST ID / Example Shell	Title	Programming Notes	SAC		
Safety	•				• 		
60.	All Treated Subjects	IDSL standard	Patient Profile Listing of Arrhythmias		Y		
61.	All Treated Subjects	IDSL standard	Patient Profile Listing of Congestive Heart Failure		Y		
62.	All Treated Subjects	IDSL standard	Patient Profile Listing of Cerebrovascular Events/Stroke/ Transient Ischemic Attack		Y		
63.	All Treated Subjects	IDSL standard	Patient Profile Listing of Deep venous Thrombosis/ Pulmonary Embolism		Y		
64.	All Treated Subjects	IDSL standard	Patient Profile Listing of Myocardial Infarction /Unstable Angina		Y		
65.	All Treated Subjects	IDSL standard	Patient Profile Listing of Peripheral Arterial Thrombosis Embolism	Events will be provided only when a related AE sequence number is present (Section 10.6.4).	Y		
66.	All Treated Subjects	IDSL standard	Patient Profile Listing of Pulmonary Hypertension		Y		
67.	All Treated Subjects	IDSL standard	Patient Profile Listing of Revascularization		Y		
68.	All Treated Subjects	IDSL standard	Patient Profile Listing of Valvulopathy		Y		
69.	All Treated Subjects	IDSL standard	Patient Profile Listing of Deaths		Y		

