10.6.5 Pharmacokinetic	
 
Derivation of tablet strength was clarified.
 
Derivation of dose level was updated to see whether PK sampling date is included within a period of exposure for each visit as follows:         
 
Treatment Start Date ≤ Date of last dose taken prior to PK sampling ≤ Treatment Stop Date
 
 
 
	
 
Clarification
 
To make sure that the derivation can apply to an irregular PK sampling such as sampling at unscheduled visit within
 
	

Reporting and Analysis Plan_204716_Amendment_Final_V1.1 [11-Oct-2017]			
Section # and Name	Description of Change	Brief Rationale	
	Dose level is derived from actual dose of a visit which meets the above exposure record.	allowance of visit window.	
10.8 Appendix 8: Values of Potential Clinical Importance	PCI values were updated in Section 10.8.1.	To maintain consistency between global and Japan Ph3 program, use the same PCI cut off values.	
10.14 Appendix 14: List of Data Displays	
 
The following bullets were modified:
 
General Changed from 'Randomized population' to 'Assigned population'
 
Table 1.9, Listing 6 Corrected title from 'Exclusions from Randomized Population' to 'Exclusions from All Treated Subjects Population'
 
Table 2.13, 2.14, 2.19, 2.20, 2.43 to 2.46, 3.27, Figure 3.1 Corrected titles
 
Table 2.47, 2.48 Added summary tables for number (%) of subjects with each dose level by visit
 
Table 3.18, 3.19 Corrected example shell ID
 
Table 3.42, 3.43, 3.44 Excluded statement to non-dialysis in Programming Notes of Vital Signs
 
Listing 2,3, 22 Corrected analysis population
 
Listing 16 Added iron parameter listing
 
Listing 25 Deleted duplicate (listing 39) and updated IDSL example
 
Listing 38, 39 Modified titles
 
Listing 65 Added programming notes
 
	Corrections and Clarifications	

Reporting and Analysis Plan_204716_Amendment_Final_V1.2 [29-NOV-2017]		
Section # and Name	Description of Change	Brief Rationale
6.1 Overview of Planned Analyses	Modification was made for the title; from 'Baseline Dialysis' to 'Baseline Mode of Dialysis'	Correction

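### SAP 10.6.4 and the Listing 65 programming note state opposite conditions for which peripheral arterial thromboembolism records are listed

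*SAP*

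**What the plan says.** SAP 10.6.4, under CV Events, sets a default and one exception: "Basically, patient profiles of CV events will be provided according to records captured in eCRF, except for Peripheral Arterial Thrombosis Embolism (PAT) form". For that form it gives a selection rule, "CV events in PAT form will be provided only when a related AE sequence number is not present", and a reason, "This is because several records in PAT form are captured just for AESI information, instead of CV events".

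SAP 10.14.12 defines the display itself. Listing 65 is the "Patient Profile Listing of Peripheral Arterial Thrombosis Embolism", on the All Treated Subjects population, and its programming note reads "Events will be provided only when a related AE sequence number is present (Section 10.6.4". None of the other patient profile listings (60 to 64 and 66 to 69) carries a filter.

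Three further places bear on the reading:

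- Protocol 7.4.1.4 explains how these forms arise: "The CV CRFs are presented as queries in response to reporting of certain CV Medical Dictionary for Regulatory Activities (MedDRA) terms". Protocol 12.6.3 names peripheral arterial thromboembolism among the events that need a cardiovascular CRF page.
- SAP 10.6.4 includes thromboembolic events in one of the AESI categories: "Death, MI, stroke, heart failure, thromboembolic events, thrombosis of vascular access".
- The amendment log in SAP 10.16 records for V1.1 both an update to 10.6.4 on PAT-form profiles and "Listing 65 Added programming notes". For V1.2 it records, under 10.6.4, a correction to how PAT-form events are displayed, without saying what changed.

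**The concern.** A programming note that points to a derivation section should repeat that section's rule. This one reverses it. A programmer working from the display list and a second working from the derivation text would each follow the SAP exactly and would not agree on a single record.

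The filter exists to keep cardiovascular events in the listing and AESI-only records out. Applied in the wrong direction, it does the opposite. With 22 subjects planned for enrolment, PAT records may be few, so an inverted filter could leave the listing empty or filled only with records it was meant to exclude. Such a listing would not look wrong to someone reading the study report.

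**Working it through.** No sample size, rate or interval enters this point, and the plan gives no figure to reproduce. The check sets the two rules side by side and follows the logic.

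**The rules**

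| Source | A PAT record is listed if its related AE sequence number is |
|---|---|
| SAP 10.6.4, CV Events | absent |
| SAP 10.14.12, Listing 65 note (citing 10.6.4) | present |

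**Records selected.** Let k be the number of PAT records and m the number that carry a related AE sequence number. Neither is given in the documents.

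- 10.6.4 lists k − m records.
- The note lists m records.
- The overlap is 0, and (k − m) + m = k, so each record appears under exactly one rule.

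**Limiting cases**

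- m = k (every record linked): 10.6.4 gives an empty listing and the note a complete one.
- m = 0 (no record linked): the reverse.
- 0 < m < k: each rule gives a partial listing, and the two share nothing.

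**Against the stated purpose.** Assume, as the SAP's reasoning implies, that the presence or absence of the AE number separates AESI-only records from cardiovascular events. Then one rule lists all the cardiovascular events and no AESI-only record, and the other lists every AESI-only record and no cardiovascular event. If the separation is imperfect, both listings are mixed but still do not overlap.

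**Which rule is intended.** The SAP never says which value marks an AESI-only record. Two pieces of evidence point in different directions:

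- *For absent (10.6.4).* V1.1 touched both passages. V1.2 corrected 10.6.4 and logs no change to Listing 65; its entries naming the display list concern two added drug-related AE tables and the new scatter plots. The note may therefore be left over from V1.1. But the log does not give the direction of the correction, and it states that minor wording changes are not recorded.
- *For present (the note).* Under Protocol 7.4.1.4 a cardiovascular form is prompted by a reported AE term, so a genuine cardiovascular event would be expected to link to an AE.

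Both are inferences. The text does not settle the matter.

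**The case against.** The strongest defence is that this is a stale cross-reference in a descriptive listing. The note defers to 10.6.4 by citing it, 10.6.4 was the passage corrected later, and a careful programmer would follow the section over the note. That is a plausible reading and may be right. It does not remove the contradiction, because the direction of the correction is not recorded and the way the forms are triggered argues the other way.

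The rest of the defence concerns reach, and it stands. A reader might infer that reporting of thromboembolic events as a whole is compromised. The documents do not support that:

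- AESIs are selected by case-by-case review and reported in Tables 3.22 to 3.24 and Listing 25. Nothing in the SAP derives those from Listing 65.
- An event linked to an AE still appears in Listing 17, the listing of all adverse events. What would be missing is the detail from the cardiovascular form.
- Stroke and transient ischemic attack (Listing 62), venous thrombosis and pulmonary embolism (63) and myocardial infarction (64) have their own unfiltered profiles.

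One small gap remains: for a PAT record with no AE number, the SAP does not say where else it would be shown.

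A reader might also take the filter itself as the fault, because it leaves records out. The SAP gives a reason for the filter, and excluding AESI-only records is its purpose. Nor must each rule leave something out: if all of the records are linked, or none, one of the rules lists every record.

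**Conclusion.** The contradiction is real and lies in current text. It is not a difference between the amendment log and the body of the SAP. As written, one of the two stated rules selects the wrong records for Listing 65. The conclusion that it would show AESI-only records in place of cardiovascular events rests on the assumption that the AE sequence number does separate the two kinds.

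The size cannot be put in numbers. It would be unsupported to say that half the records are lost, because neither the number of PAT records nor the linked share is given. It would also go too far to say that the Listing 65 note is certainly the passage in error.

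Severity is minor: one patient-level listing is affected, and no table, rate, interval or endpoint is shown to use this rule.

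**What to change.** Before database freeze, the sponsor should confirm the intended direction, edit whichever passage is wrong so that 10.6.4 and the Listing 65 note give the same condition, and add a sentence to 10.6.4 saying which value of the AE sequence number identifies a record captured only for AESI information. The amendment log should record the direction of the change.

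The cost is a one-word edit and one added sentence, with no new data or analysis.

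Optionally, Listing 65 could show every PAT record with its AE sequence number and an AESI-only flag. That is a design preference and is not needed to resolve the contradiction.
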